For all phases of the study, patients are recruited based on being in treatment for a serious mental illness, being at risk of symptoms, and using a mobile phone. Participants will receive assessments from a research assistant at baseline and follow-up. This baseline and follow-up assessments will be conducted by a research assistant. Patient interviews assess recent medication adherence, housing status, substance abuse, psychiatric symptoms, cognitive deficits associated with SMI, and functioning. In addition, each week, research staff will contact participants by phone, and administer brief assessments of sociability, activity, sleep, and mood and psychotic symptoms. At the conclusion of the study period, the participant will come to the VA to meet with research staff for a final quantitative follow-up interview which includes the same measures from the baseline assessment. At 3 and 9 months, a semi-structured interview is conducted with a subsample by phone to elucidate the feasibility, acceptability and safety of mobile sensing. At the end of the study period, the app will be deleted from the phone, and the participant will be notified that it is no longer functional.

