#### *Weekly research assessments*

Sociability: Social withdrawal and functioning will be assessed using the Abbreviated Lubben Social Network Scale (6 items) and the Objective Frequency of Social Contact scale (6 items).

Activity: Physical activity, routines and habits will be assessed using the Short International Physical Activity Questionnaire (4 items) and the Independence Performance and Prosocial domains of the Social Functioning Scale (15 items).

Sleep: Sleep duration and quality will be assessed using components 1, 2, 3 and 6 from the Pittsburgh Sleep Quality Index (5 items) and the Insomnia Problem items from the Insomnia Severity Index (3 items).

Symptoms: Symptom severity will be assessed using the Brief Psychiatric Rating Scale. We will use the BPRS Positive Symptoms Factor (psychosis), Activation Factor (mania), and Affect Factor (depression) (9 items total).

Safety: We will monitor adverse events on a weekly basis using data from weekly assessment phone calls and the medical record. Based on prior research studies of mobile sensing in people with SMI, and our prior mobile informatics research in patients with SMI at VA, we do not expect any safety problems.

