#### *Data Collected from Mobile Application*

The app collects passive behavioral data for assessment in three domains that have previously been proven to be measurable using these data: sociability, activities, and sleep. Sensor data collected from the app is encrypted and cached locally on the device, securely transmitted to the platform's remote server when a data connection is available. Analyses will seek to correlate behavioral patterns with emotional well-being. Analyses will also conduct time-series analysis to monitor shifts over time. We

anticipate detecting acute health stress through shifts in behavior patterns. The app will passively collect behavior data in three domains: sociability, activity, and sleep.

Participants will be able to view the tracking of their activities, sociability and sleep over time, similar to how people currently view their step counts in mobile health app dashboards. Each of the behavioral domains in this project will be presented on a 1-100 scale, as numbers graphed over time.

Sociability explores social characteristics of the individual. Dynamic and active social lives are correlates of mental health. Concurrently, sudden changes in sociability, particularly a notable increase in introversion and isolation could be indicators of diminishing mental health. Sociability assesses social characteristics by collecting information on calls and texts made with the phone (the content of these communications is not assessed or recorded) and public interaction by measuring ambient sound in social environments. Specific measures of Sociability we will attempt to gather:

- Communication: regular communication with a diverse set of individuals by phone call, text messaging, or use of messaging apps
- Public Interaction: regular communication with others in person or spending time in a social environment

Activity measures an individual's day-to-day routine by monitoring activity, movement, location, and habits. Adhering to regular routines, engaging in exercise, and productive activity outside the home are indicators of mental health. Changes in routines, lack of exercise, and limited intentional movement outside the home can be signs of mental health issues. Specific measures of Activity we will gather:

- Routine: a regular and structured daily and weekly routine
- Exercise: regular exercise
- Activities: Engagement in activities, particularly outside of the individual's residence

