Using multivariate analyses, we study whether quantitative baseline patient characteristics described above are associated with feasibility, acceptability, and safety. Qualitative data from patients 3-month and 9-month interviews are used to evaluate themes related to the feasibility, acceptability and safety of sensing. Qualitative data from post-intervention clinician interviews are used to evaluate themes related to patient engagement, findings, implementation, and resources for sustainability and incorporation into routine practice. Using ATLAS.ti, transcripts of interviews will be coded deductively for major subthemes regarding acceptability, strengths and weaknesses, barriers and facilitators of use, safety, and recommendations about future revisions and implementation efforts. The qualitative findings will be triangulated with findings from the other measure of acceptability and safety to examine whether concordance exists among these measures of the intervention. Should analytic anomalies in the quantitative findings arise, the qualitative data will be explored to illuminate possible explanations for unexpected findings. At 3 and 9 months, 26 individuals should be sufficient to provide data saturation regarding acceptability of the intervention using qualitative data.

Aims 3 & 4. Use mobile sensor and phone utilization data to develop individualized estimates of sociability, activities, and sleep as measured by weekly interview. Study the predictive value of using data on sociability, activities, and sleep to identify exacerbations of psychiatric symptoms.

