In Aim 3 we develop individualized estimates of sociability, activities and sleep. We will aggregate daily mobile data on a weekly basis to predict behavioral measures that are also obtained weekly. Summary statistics such as mean, variance, min, or max will be used for aggregation as deemed appropriate. We will then employ various machine learning algorithms to build, train, and select prediction models for each of the patient behavioral assessment domains using features of sensor and phone utilization data (Table 1). Model development will proceed in three stages. First, we will utilize methods of unsupervised learning to cluster sensor and phone utilization data and extract features to reduce the dimensionality. Second, we will explore a number of supervised learning procedures to build candidate prediction models for patient behavioral assessments. Finally, we will use cross-validation to estimate the out-of-sample performance of the prediction models, and to select best model(s) from among the candidates.

To reduce the number of features upon which to build the prediction models, while preserving the maximum amount of information, the first strategy is to use principal component analysis (PCA). PCA reduces the dimensionality of a data set by identifying linear combinations of the features, the principal components, which maximize variability while remaining mutually uncorrelated. Building the models using fewer candidate features reduces the risk of overfitting, and using the principal components in place of the original features prevents problems of multicollinearity. The second dimension reduction strategy is to use FDR (false discovery rate) threshold. FDR-based thresholding gives an optimal way of adapting to unknown sparsity (only a small number of effects are significantly large) and may be viewed as an estimation procedure with an appropriate penalization scheme accounting for the number of selected variables.

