Given the reduced number of features, various supervised machine learning algorithms will be used to train prediction models for patient behaviors and symptoms. At the preliminary analysis stage, a set of supervised learning algorithms will be explored to evaluate cross-sectional associations between mobile data features and patient behavioral assessments, with the goal of narrowing down the pool of candidate predictors. First, we will consider random forests. A random forest is a collection of decision trees, each built using a random sample of features, and trained on a bootstrap sample from the original data. Random forests are useful for identifying complex interactions among features due to the use of decision tree learning, while protecting against overfitting by means of bootstrap aggregation. Second, we will consider support vector machines (SVM). SVM is a method of supervised learning which classifies instances into categories by estimating a hyperplane that separates instances belonging to different classes. SVM may be used if the outcomes of interest, behaviors and symptoms, can be meaningfully categorized (e.g., high vs. low). Selected predictors from these approaches will be used in the next step of the model building process that takes into account the temporal correlation and time series nature of mobile data and patient assessments. We will use hidden Markov models to predict patients' current behaviors and symptoms based on current features and past patients' behaviors and symptoms. We view patients' features as observed states, and patients' behaviors and symptoms are hidden states that enjoy the Markov property. We will also use linear or generalized linear mixed effects models to predict patient behavioral assessments using selected features from the preliminary stage, while taking into account within-patient correlation in repeated measurements over time.

Models developed using supervised machine learning methods will be evaluated in terms of out-of-sample predictive performance using leave-one-out cross-validation (LOOCV). For time series modeling, models will be trained on times 1, ..., t-1, and evaluated on time t, for each time t. For cross-sectional modeling, models will be trained on all but patient i, and evaluated on patient i, for each patient i. Performance will be averaged across hold-out times/patients to obtain a LOOCV estimate of

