generalization error. Quadratic loss will be used to evaluate prediction error. The selected model will be the one that minimizes LOOCV mean squared error.

In Aim 4, outcome data are collected weekly for each patient on three scales (psychosis, mania, depression). These scales each have a range of 1 to 7. The primary outcome will be the scale indicating the most severe symptoms in a 2-month window. We will evaluate the association between mobile data features identified in Aim 3 with this primary outcome using a mixed effects model to accommodate within patient data correlation due to repeated measures. Specifically, we will consider feature data from fixed time windows preceding the most severe symptoms. The outcome data distribution will be examined prior to model fitting, and an appropriate link function will be used in the mixed effects model.

Sample size and power considerations: In Aim 3, we extract features of mobile sensor and phone utilization data to estimate behaviors in the domains of sociability, activity, and sleep. The selected features should have a high correlation with behaviors to be a good estimate. Of 100 participants enrolled, assuming 30% attrition, we expect to have complete data on 70 participants (and substantial longitudinal data for a larger group). This sample size will provide over 95% power to detect a correlation of at least 0.50 at the significance level 0.05 using a two-sided test. In Aim 4, our inclusion criteria select for greater than average symptom risk, so we anticipate substantial symptoms. Previous research on 21 patients with SMI for a median of 134 days found that sensing data predicted symptom indicator scores with correlations in the range of 0.5 to 0.8. Given possible confounders, and since our sample may be more heterogeneous than prior research, the correlation in our study is anticipated to be lower than what was reported previously. With 100 enrolled, and assuming 30% attrition, we will have over 85% power to detect correlations of at least 0.35 between predictors of interest and symptoms assessments at the significance level of 0.05 using a two-sided test.

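### Does letting participants see their own app scores spoil Aim 3's comparison of sensor estimates with weekly self-report?

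*Combined protocol and SAP*

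**What the plan says.** Under Data Collected from Mobile Application, participants get a dashboard: "Participants will be able to view the tracking of their activities, sociability and sleep over time". On its form: "Each of the behavioral domains in this project will be presented on a 1-100 scale, as numbers graphed over time". The second objective at the start of the protocol makes returning status information to the Veteran part of what is studied.

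Under Methods, "each week, research staff will contact participants by phone, and administer brief assessments of sociability, activity, sleep, and mood and psychotic symptoms". The section on weekly research assessments lists the instruments. They are multi-item questionnaires on social network and contact, physical activity and social functioning, and sleep and insomnia, plus the BPRS for symptoms.

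Under Data Analyses, Aim 3 is to "develop individualized estimates of sociability, activities, and sleep as measured by weekly interview". The method follows: "We will aggregate daily mobile data on a weekly basis to predict behavioral measures that are also obtained weekly". Candidate models are compared by leave-one-out cross-validation, holding out times or patients, and "The selected model will be the one that minimizes LOOCV mean squared error".

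The analysis text for Aims 1 and 2 counts days of dashboard use as a measure of acceptability. The Aim 3 text has no covariate, stratum or sensitivity analysis for dashboard viewing.

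**The concern.** A reference measure should be obtained independently of the thing it judges. Here the person answering the weekly questions may just have looked at a graph built from phone data on the same domain. If the graph pulls the answer toward itself, the agreement between sensor features and interview rises without the sensors having become any better.

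Cross-validation would not show this, because the held-out reports come from people with the same dashboard. Aim 4 takes over the features identified in Aim 3, so a distorted choice of features could be carried forward. The plan also counts days of dashboard use, so it looks as though it holds the means to check and does not use them. At stake would be the stated accuracy of the behavioural estimates.

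**Working it through.** **1. The plan's own figure.** The sample size section gives 70 completers (100 enrolled, 30% attrition), a correlation of 0.50 and a two-sided level of 0.05. Fisher's z gives power = Φ(atanh(0.50) × √67 − 1.960) = Φ(4.496 − 1.960) = Φ(2.536) = 99.4%. This agrees with the stated power of over 95%. The figure is not in dispute.

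**2. What Aim 3 claims, beside what is displayed.** The target is the interview measure. The population is people who carry the app and can see the dashboard. The product under study is self-tracking with feedback. Agreement under feedback is therefore the quantity that the design estimates. The plan makes no claim about accuracy in people without a dashboard.

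**3. How large could anchoring be?** Only r = 0.50 comes from the documents. Everything else in this step is assumed.

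Let S be the feature, R the unaided answer and D the displayed score, all standardized, with corr(S,R) = corr(D,R) = r and corr(S,D) = d. In a viewed week the answer is (1−w)R + wD, and a share p of weeks is viewed.

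- Variance in viewed weeks: v = (1−w)² + w² + 2w(1−w)r, which is 0.91 for w = 0.1 and 0.84 for w = 0.2.
- Slope in viewed weeks: b = (1−w)r + wd.
- All weeks: V = 1 − p + pv and B = (1−p)r + pb. The correlation is B/√V and the mean squared error is V − B².
- With no viewing, the mean squared error is 1 − 0.25 = 0.750.

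With half the weeks viewed (p = 0.5):

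| w, d | V | B | Correlation | MSE | Fall in MSE | Share of fall due to lower V |
|---|---|---|---|---|---|---|
| 0.1, 0.5 | 0.955 | 0.500 | 0.512 | 0.705 | 6% | 100% |
| 0.2, 0.5 | 0.920 | 0.500 | 0.521 | 0.670 | 11% | 100% |
| 0.1, 0.8 | 0.955 | 0.515 | 0.527 | 0.690 | 8% | 0.045/0.060 = 75% |
| 0.2, 0.8 | 0.920 | 0.530 | 0.553 | 0.639 | 15% | 0.080/0.111 = 72% |

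With a quarter of weeks viewed, the correlation is 0.51 to 0.53 and the mean squared error falls by 3% to 7%.

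The drop in V is common to every candidate model, so that part cannot change which model is selected. Only B² can differ between candidates. In the largest case of the table it rises from 0.250 to 0.281.

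The extreme of the same formula sets d = 1 (the display is the feature itself) and p = 1 (viewed before every call). For w = 0.1 the correlation is 0.55/√0.91 = 0.58, and for w = 0.2 it is 0.60/√0.84 = 0.65. The lower variance then explains 0.090/0.1425 = 63% and 0.160/0.270 = 59% of the fall in mean squared error.

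The documents do not say how the displayed score is computed, how often it is viewed, or how it relates to any questionnaire item. They cannot place the trial anywhere in this range.

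**4. Would comparing viewed and unviewed weeks settle it?** Viewed-week correlations in the four tabulated cases are 0.524, 0.546, 0.556 and 0.611, so the gaps from 0.50 are 0.024, 0.046, 0.056 and 0.111. A simulation of 70 × 39 = 2,730 person-weeks (1,000 runs, assumed intraclass correlation 0.5 and person-slope SD 0.2) gives:

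- power of 5% to 31% for gaps of 0.02 to 0.05;
- for a gap of 0.11, power of 72% to 96% if viewing varies within person, or 57% if only 10% of weeks are viewed and 70% of calls are completed;
- for a gap of 0.11, power of 12% to 22% if viewing is fixed by person.

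Viewing is also self-selected, and may itself sharpen recall.

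**5. Aim 4.** Its outcome is built from the psychosis, mania and depression scales of the BPRS. None of these is on the dashboard, so anchoring to displayed domains does not directly inflate that association.

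**The case for a change.** The strongest case for the concern is that predictor and reference may not be independent and that neither hold-out scheme can reveal it. Dashboard days are to be counted anyway, so a sensitivity analysis would cost little, whereas viewing dates that are not kept cannot be recovered. A feature-by-viewing interaction alone would not do: with w = 0.2 and d = 0.5 the slope gap is zero while the viewed-week correlation rises to 0.546.

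Much of this stands. The Aim 3 text has no term for viewing. Table 1 lists apps opened and duration of app use among the sleep inputs, which might pick up use of the study app, but that is no adjustment for having seen a score. Cross-validation is indeed blind to anchoring. If the display were the predictor itself, the inflation would not be trivial.

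The step to a fault does not stand. The mechanism needs a 1-100 graph to move answers to staff-administered items on contacts, activities and sleep, and the documents give no mapping between them. Real behaviour change after feedback would appear in both measures and need not bias their agreement. The comparison would leave the primary analysis unchanged and depends on dated viewing records that the documents do not confirm. The monthly count under Formative evaluation assessments covers recording and transmission, not viewing. A null result would not reassure, and a positive one would not identify anchoring.

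**Conclusion.** The concern does not hold. The plan studies passive tracking with feedback and defines its Aim 3 target as the weekly interview measure, so estimating agreement among people with dashboard access is what it sets out to do. Following it as written produces no wrong result.

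Anchoring is possible but not established. Under assumed weights of 10% to 20%, the planning correlation of 0.50 would become 0.51 to 0.55 with half the weeks viewed, and 0.58 to 0.65 at the extreme. In the tabulated cases, 72% to 100% of the fall in mean squared error is lower outcome variance, which does not affect the choice of model.

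An analysis by viewing would be a reasonable extra, but its absence is not a defect. The conclusion rests on reading Aim 3 as agreement with self-report under feedback. It would not extend to a later claim of accuracy in people who have no dashboard.

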### Patient Participant Assessments and App Download

For participants in the mobile sensing trial, after the informed consent process, research staff administer the baseline research assessment. Then the project app is downloaded to the participant's

phone. It is activated by staff using a code. Each time the app is activated on a device, a unique ID is created by the server. This ID connects data from the app with patient identifiers kept on the secure server. After the app is activated, it runs in the background and collects data passively with no further action from the user.

Participants will receive phone calls from study staff on a weekly basis throughout a 9-month study period to complete assessments by phone. Based on our experience with these assessment instruments, as staff get to know individual patients the time required for assessments becomes relatively brief. A semi-structured qualitative interview will also be conducted at 3 months by phone with a subsample of participants until data saturation is achieved. At the conclusion of the 9 month study period, the participants meet with research staff for a final follow-up interview. At this point, the project app will be deleted from the phone, and the participant will be notified that it is no longer functional. The final assessment will also include a qualitative component for a subsample of participants until data saturation is achieved.

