### Baseline and Final Follow-up

Demographics: Demographic data including age, race, ethnicity, marital status, educational attainment, annual family income, and household roster; and psychiatric illness history will be collected from the patient at baseline only.

Phone data plan: Phone data plan information will be collected from each patient's recent phone bill brought to the baseline assessment. We will also collect their phone number.

Psychopathology, Substance Abuse, Cognitive Deficits, Functioning: Psychopathology will be measured using the Brief Psychiatric Rating Scale (BPRS) at both baseline and 9 month follow-up. Psychopathology will be measured using the Brief Psychiatric Rating Scale (BPRS). We will use the BPRS Positive Symptoms Factor (psychosis), Activation Factor (mania), and Affect Factor (depression) (9 items total).

Cognitive deficits of SMI will be measured by brief assessment. We will assess verbal learning using the Hopkins Verbal Learning Test-Revised (HVLT-R), and processing speed using the Digit Symbol Coding Test at baseline only. Occupational, social, symptom-related and overall functioning will be assessed using the MIRECC GAF at baseline only, which has been validated in Veterans with SMI.

Housing Stability: Housing stability for the past 30 days will be assessed using the Residential Time-Line Follow-Back Inventory (RTLFB). The RTLFB has been used in prior research to collect retrospective housing history over a specified period of time among people who have experienced homelessness. All residences over 30 days will be recorded, and coded into one of 34 previously defined locations, which will be further categorized as "stable" (e.g., own apartment, room or studio apartment in a supportive housing program, transitional housing, group home, boarding home) versus "unstable" (e.g., living on the streets, in public places, in emergency shelter-type accommodations) settings, using established methodology. The number of days spent in any of the locations categorized as "stable" or "unstable" will be summed and divided by the total number of days of residency reported at the interview,

and reported as a percentage. RTLFB has been demonstrated sensitive to change. This will be collected at baseline only.

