Sleep total sleep duration uninterrupted sleep regular daily sleep and wake times	Sleep: 
 
ambient light sensor: indoors, outdoors or dark location
 
ambient sound sensor: volume
 
significant motion Android software: motion leading to change in location
 
Fused Location Google API (uses GPS & wifi): location after 5 meters of movement
 
phone unlock, screen interactions and on-time duration
 
log of phone calls placed
 
log of messages sent
 
apps opened
 
app duration of use
 
	
 
Pittsburgh Sleep Quality Index Components 1, 2, 3, 6 (5 items)
 
Insomnia Problem items from the Insomnia Severity Index (3 items)
 

Sociability communication in person or in a public social environment communication with a diverse set of individuals communication with repeated partners	
 
log of phone calls placed with phone numbers
 
log of phone calls received with phone numbers
 
log of messages sent with phone numbers
 
log of messages received with phone numbers
 
social media apps opened
 
social media apps: keystrokes and duration used
 
messaging or email apps opened
 
messaging or email apps: keystrokes and duration used
 
ambient sound sensor: volume
 
Activity Recognition Google API: still, on foot
 
Fused Location Google API (by GPS & wifi): location after 5 meters of movement
 
	
 
Objective Frequency of Social Contact scale (6 items)
 
Abbreviated Lubben Social Network Scale (6 items)
 

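### No preprocessing step removes the weekly study calls, so calls that reach the app phone are counted as the participant's sociability

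*Combined protocol and SAP*

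**What the plan says.** **The contact.** Patient Participant Assessments and App Download states: "Participants will receive phone calls from study staff on a weekly basis throughout a 9-month study period to complete assessments by phone". Methods says that "research staff will contact participants by phone, and administer brief assessments of sociability, activity, sleep, and mood and psychotic symptoms". The protocol expects that "as staff get to know individual patients the time required for assessments becomes relatively brief", but gives no minutes.

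**The phone.** The same section places the app on the participant's own device ("Then the project app is downloaded to the participant's" phone) and adds: "After the app is activated, it runs in the background and collects data passively with no further action from the user". No pause for study calls is described. Owning a phone with a data plan is an inclusion criterion, the phone is brought to the consent visit, and Baseline and Final Follow-up says: "We will also collect their phone number". No section states that this number is the one dialled each week.

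**The inputs.** In Table 1 (Data Collected from Mobile Application), Sociability uses logs of calls and messages in both directions with phone numbers, including "log of phone calls received with phone numbers", and ambient sound volume. Contact with repeated partners is one of its constructs. Sleep uses "phone unlock, screen interactions and on-time duration", sound volume and a log of placed calls, but not received calls.

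**The processing.** Data Analyses names total phone calls as a daily summary and aggregates daily data to the week, the same unit as the assessment. It discusses thresholds, alignment and missing data. It has no rule for calls that the study itself generates. Participants see each domain on a 1-100 scale.

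**The concern.** The process that collects the outcome can leave a trace in the predictor. A weekly staff caller looks to the app like a regular social contact. For an isolated participant this could be a sizeable part of the logged calls, and it would be absent in routine use, where nobody makes research calls.

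There are two consequences to separate. The first is level: call features, and any displayed sociability score built on them, are higher than the participant's own behaviour warrants. The second is association: if staff try more often in weeks when a participant is unwell, and those attempts are logged, call counts rise with symptoms through staff action. That could create a weak association. It could also offset a real fall in contact, which the protocol regards as a warning sign.

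**Working it through.** **1. Volume of study contact.** Calls: 9 × 52/12 = 39 per participant. Items per call, from Weekly research assessments: 6 + 6 + 4 + 15 + 5 + 3 + 9 = 48.

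**2. The plan's own figures.** Power for a correlation by Fisher z is Φ(atanh(r)·√(n−3) − 1.96) with n = 70.
- r = 0.50: 0.5493 × √67 − 1.96 = 2.536, power 99.4% (plan: over 95%).
- r = 0.35: 0.3654 × √67 − 1.96 = 1.031, power 84.9%; simulating the two-sided t test gives 85.6% (plan: over 85%).

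Both are reproduced. They depend only on n, r and alpha, so removing study calls changes neither.

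**3. Effect on level.** The documents give no call volumes, so other received calls per week (m) are assumed. With k logged study calls, their share is k/(k + m).

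| Other received calls per week | 2 | 5 | 10 | 20 | 40 |
|---|---|---|---|---|---|
| One study call | 33% | 17% | 9% | 5% | 2% |
| Three logged attempts | 60% | 38% | 23% | 13% | 7% |

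**4. One regular answered call.** It adds the same constant to every week, and adding a constant leaves a correlation unchanged. Simulation of a weekly fixed-effects regression with no dependence of attempts on symptoms gave 4% to 6% rejection at a nominal 5%.

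**5. Attempts that follow symptoms (assumed).** Let own calls be Poisson with mean m, and study calls be 1 + Poisson(a + d·p), where p is the within-patient symptom percentile, uniform on 0 to 1. All attempts are taken to be logged. The induced within-patient correlation of count with p is

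r = (d/√12) / √(m + a + d/2 + d²/12).

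Mild: mean extra attempts rise from 0.25 to 0.75 (a = 0.25, d = 0.5). Strong: from 0.25 to 1.75 (d = 1.5).

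| Own calls per week (m) | 3 | 5 | 10 | 20 |
|---|---|---|---|---|
| Mild: study share of calls | 33% | 23% | 13% | 7% |
| Mild: induced r | 0.08 | 0.06 | 0.04 | 0.03 |
| Strong: induced r | 0.21 | 0.17 | 0.13 | 0.09 |

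Example, mild, m = 3: 0.1443/√(3 + 0.5 + 0.0208) = 0.077.

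**6. Overdispersed own calls.** With a negative binomial (k = 2), m in the denominator becomes m + m²/2. Induced r falls to 0.05, 0.03, 0.02 and 0.01 (mild) and to 0.15, 0.10, 0.06 and 0.03 (strong).

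**7. Variation unrelated to symptoms.** This only adds noise: r is divided by √(1 + v), where v is the study-call variance relative to the genuine feature variance. At v = 0.05, 0.35 becomes 0.35/√1.05 = 0.342.

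**The case against.** Much of the case on the other side stands.

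- **The phone is inferred.** No section says that the weekly call goes to the app phone, or that study calls are kept. Table 1 lists raw inputs and the preprocessing text is high-level. The inference is still strong, because no other contact line is mentioned.
- **Attempts may not be logged.** The input is calls received, and the documents do not say whether unanswered attempts count. If only answered calls count, each assessed week has about one study call, and a week without an assessment has no weekly outcome to model. Nothing in the documents links attempts to symptoms.
- **Call length.** A reader might infer that shortening calls put a trend into call-duration features. Table 1 lists no call duration, so length could act only through screen use and sound.
- **Sleep.** An incoming study call is not in the Sleep call log. A daytime call should matter little to sleep features; only call-backs by the participant would appear there.
- **False-positive rates.** A reader might infer that a spurious call feature is almost sure to be selected. In a weekly regression on 70 × 39 = 2,730 patient-weeks, the mild case does give rejection rates of about 38% to 99%, but this mainly reflects the number of weeks. Aim 3 selects models by cross-validated squared error. Aim 4 uses the worst scale in a 2-month window with features from preceding windows. A rough version of Aim 4 (four 9-week windows, calls from the two weeks before the peak, mild case) gave 3% to 5% with independent weekly symptoms, and 6% to 18% with week-to-week correlation 0.7. The documents do not support the near-certain reading.

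What the objection does not answer is the absence of a rule. Silence leaves study calls in the data, and the effect on level needs no assumption about symptoms.

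**Conclusion.** The point holds in a limited form. Followed as written, the plan counts study calls that reach the app phone as sociability. The sure effect is on level: call features, and any 1-100 sociability score built on them, are raised, most for participants with few other calls. A regular answered call does not by itself bias a within-patient association.

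A created or hidden association in Aims 3 and 4 arises only if repeat attempts, call-backs or missed calls are logged and vary with symptoms. Its size cannot be derived from the documents. Under the stated assumptions it is small beside the planned correlations of 0.35 and 0.50 in the mild case, and reaches 0.21 only with strong dependence and few own calls. No sample-size or power statement is wrong. The Sleep part is minor. This is a cheap improvement to the preprocessing, not a flaw that undermines the trial.

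**What to change.** In the data preprocessing phase under Data Analyses, state that all calls and messages to or from study phone numbers are dropped before any Sociability or Sleep feature or dashboard score is computed. This should cover retries, voicemails and call-backs. State also that screen-use and ambient-sound data are masked for the duration of each study call.

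The call and message logs used for Sociability already hold phone numbers, and staff can record call times. The cost is one filter rule, a maintained list of study numbers and call times, and a few minutes of masked sensor time a week. No further participants, visits or measurements are needed.
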